Email: [contact]

PRÉCIS

Study Title

Optimization of Spinal Manipulative Therapy (SMT) Protocols

Objectives

Primary Aims

[figure not shown]
- I. Identify SMT protocol components and interactions that independently predict SMT mechanistic outcomes (spinal stiffness and multifidus activation). We hypothesize that one or more combination of components will be identified that optimize improvement in SMT mechanisms.
- II. Identify SMT protocol components and interactions that independently predict SMT patient-centered outcomes (function, pain). We hypothesize that one or more combination of components will be identified that optimize improvement in patient-centered outcomes.

Secondary Aims

- I. Explore the moderating effect of responder status after 2 SMT sessions. We hypothesize that responder status after 2 sessions will moderate mechanistic and patient-centered outcomes.
- II. Define optimized SMT protocol(s) based on combined results of the primary and secondary aims. Optimized protocols will be considered as the combination of components that maximize improvement in patient-centered outcomes at 3 months while also improving SMT mechanisms to the greatest extent.

Design and Outcomes

This subject will recruit adults with non-specific low back pain (LBP). We will provide 2 sessions of SMT to all subjects. We will then assess responder status and randomize subjects stratified by responder status to a treatment group for an additional 3 weeks using a factorial design to evaluate different combinations of intervention components (muscle activation exercise, spinal mobilizing exercise, additional SMT) that influence pathways shown to modulate the effects of SMT. Outcomes will include spinal stiffness and muscle activation measures as well as patient-reported outcomes assessed at baseline, and after 1 week, 4 weeks and 3 months.

Outline of research design (LM = lumbar multifidus)

Interventions and Duration

All subjects will receive 2 sessions of SMT provided in the first week of participation. Subjects are then randomly assigned to receive an additional 3 weeks of treatment involving different combinations of exercise and/or additional SMT, or to receive no additional treatment. The final follow-up is conducted 3 months after enrollment. Therefore the total time for a subject to be "on study" is 3 months.

Sample Size and Population

We will recruit a total of 316 subjects age 18-60 with non-specific LBP and an Oswestry Disability score of at least 20%. Following Phase I treatment, subjects will be randomized in equal proportions to one of 8 possible treatment combinations in Phase II. Randomization will be stratified by responder status (yes/no) during Phase I.

1. STUDY OBJECTIVES

1.1 Primary Objectives

- I. Identify SMT protocol components and interactions that independently predict SMT mechanistic outcomes (spinal stiffness and multifidus activation). We hypothesize that one or more combination of components will be identified that optimize improvement in SMT mechanisms.
- II. Identify SMT protocol components and interactions that independently predict SMT patient-centered outcomes (function, pain). We hypothesize that one or more combination of components will be identified that optimize improvement in patient-centered outcomes.

1.2 Secondary Objectives

- I. Explore the moderating effect of responder status after 2 SMT sessions. We hypothesize that responder status after 2 sessions will moderate mechanistic and patient-centered outcomes.
- II. Define optimized SMT protocol(s) based on combined results of the primary and secondary aims. Optimized protocols will be considered as the combination of components that maximize improvement in patient-centered outcomes at 3 months while also improving SMT mechanisms to the greatest extent.

2. BACKGROUND AND RATIONALE

2.1 Background on Condition, Disease, or Other Primary Study Focus

Low back pain (LBP) is a major public health problem. An estimated 60-80% of individuals will experience an episode during their lifetime, and prevalence rates have been increasing in the past decade. Considering the prevalence of LBP, it is not surprising that the condition imposes significant economic burden on individuals, the healthcare delivery system, and society. Total annual direct healthcare costs in the U.S. for LBP were estimated at \$90 billion in 1998, with an inflation-adjusted rate of 65% over the next 7 years, a rate much higher than overall health care costs. LBP is the most common symptom for which complementary and alternative medicine (CAM) is sought. In 2007, 18% of adult CAM users in the U.S. were seeking care for LBP, more than double the next most common condition. The most common CAM intervention sought by those with LBP is spinal manipulative therapy (SMT). Several professions use SMT, although it is most often provided by chiropractors. Surveys in the U.S. suggest about half of those with chronic LBP have sought chiropractic care, and LBP the reason for at least 40% of chiropractic visits. The Institute of Medicine identifies LBP as a top 15 priority condition, calling for the development of innovative, evidence-based management strategies. In light of the prevalence of LBP and the frequency of SMT use for the condition, optimizing SMT protocols for LBP has important public health implications.

2.2 Study Rationale

[figure not shown]
Successful optimization of SMT treatment requires understanding the mechanisms underlying the effects of SMT among patients who are SMT-responders. Past research has identified numerous biologic phenomena that accompany SMT without relating these phenomena to the presence or absence of clinical benefit. In contrast, our research team has worked for more than 10 years to

develop and validate a model explaining the mechanisms that underlie the clinical effects of SMT. Specifically, our work supports the common clinical observation that SMT is not a broad-spectrum therapy, but one that preferentially benefits some individuals with LBP (SMT-responders) but not others (non-responders). This work has culminated in the development of a validated model that has identified specific biomechanical signals (changes in spinal stiffness and lumbar multifidus muscle activation) that relate to favorable clinical response (improved function). The clinically important signals we have identified (stiffness and muscle activation) are modifiable with interventions other than SMT; thus SMT protocols may be optimized through the use of co-interventions that modulate these signals. Our team has also developed safe, valid and reliable procedures to measure these signals, and have demonstrated successful application of both SMT treatment and signal measurement procedures in clinical populations.

Our goal in this proposal is to optimize SMT treatment protocols for LBP. Our optimization strategy will evaluate SMT combined with other treatments known to modulate the same signals that underlie the clinical effects of SMT (spinal stiffness and muscle activation) using both mechanistic (stiffness, lumbar multifidus activation) and patient-centered (function and pain) outcomes. We have grounded our body of work in this area within the Multiphase Optimization Strategy (MOST) framework; which provides an efficient multi-step research strategy for optimizing multi-component interventions. In this project we will use innovative methodology to efficiently evaluate the effects of various individual treatment components towards an overall effect; identifying which components are contributing to the target outcomes and which, if any, may be discarded. Results of this project will provide optimized SMT protocols that will be ready for application in future randomized controlled trials examining the efficacy and effectiveness of SMT.

3. STUDY DESIGN

We will use a factorial design examining 3 intervention components (additional SMT, mobilizing and multifidus activating exercise) provided in 8 different combinations following provision of 2 SMT treatment sessions as in our prior work. We will recruit 316 subjects with non-specific LBP with the goal of enrolling 280 subjects after all eligibility screening are complete. All subjects will receive the 2-session SMT protocol used in our prior studies. At the third session subjects will be categorized as SMT responders or non-responders based on our previously-validated threshold of 50% improvement on the Oswestry (ODQ). Randomization to subsequent treatment will be stratified based on responder status. This will allow us to examine the moderating effects of early clinical response. In our prior studies 35%-45% of individuals with LBP are responders to SMT after 2 sessions. What is unknown is the persistence of the improvement observed in early responders and whether or not persistence can be augmented through additional SMT and/or co-interventions working on the same causal pathways as SMT. Likewise, it is unknown from our prior work if early non-responders can be converted to responders with additional SMT and/or co-interventions. Therefore, we will randomly assign subjects to receive 6 additional sessions (or no additional treatment) provided over 3 weeks with varied combinations of additional SMT and exercise co-interventions. We chose 6 additional sessions based on work related to SMT dose-response reporting only modest difference in clinical outcomes in subjects receiving 9-12 sessions relative to 3-6 SMT sessions without co-interventions. Outcomes including assessments of

Outline of research design (LM = lumbar multifidus)

mechanisms and patient-centered outcomes will be examined at baseline and after 1 week (end of phase I), 4 weeks (primary outcome - end of phase II), and after 3 months (long-term outcome).

4. SELECTION AND ENROLLMENT OF PARTICIPANTS

4.1 Inclusion Criteria

Subjects in this study must satisfy all of the following eligibility criteria:

- I. Pain between the 12th rib and buttocks with or without symptoms into one or both legs, which, in the opinion of the examiner, originate from the lumbar region.
- II. Age 18 - 60 years
- III. Oswestry disability score $\geq 20\%$

4.2 Exclusion Criteria

Any subject meeting any of the following exclusion criteria at baseline will be excluded from participation.

- I. No prior surgery to the lumbosacral spine
- II. Not currently pregnant
- III. Not currently receiving mind-body or exercise treatment for LBP from a healthcare provider (e.g., chiropractic, physical therapy, massage therapy, etc.)
- IV. No neurogenic signs including any of the following: positive ipsi- or contra-lateral straight leg raise test (symptoms reproduced $<45^\circ$); reflex, sensory, or strength deficit in a pattern consistent with lumbar nerve root compression
- V. No “red flags” of a potentially serious condition including cauda equina syndrome, major or rapidly progressing neurological deficit, fracture, cancer, infection or systemic disease

4.3 Study Enrollment Procedures

Participants will be enrolled at two sites: the University of Utah and University of Alberta. At the University of Utah we will work within the University of Utah Health Care (UUHC) family practice and psychiatry providers to encourage direct referral of interested individuals consulting for LBP into the study. We will also develop IRB-approved recruitment materials to be integrated into our EPIC electronic health record, allowing providers to print and provide the information to potentially-interested individuals. We will also work with the Center for Clinical and Translational Science (CCTS) Bioinformatics Core to use the UUHC electronic data warehouse (EDW) to identify patients with specific characteristics based on demographic information and ICD-10 codes. These individuals are informed of the study by mail with information on procedures to opt-in or out of the study by contacting research personnel. For this project we will identify patients with a family practice visit with an ICD-10 code related to non-specific LBP (M54.5, M54.9, M51.36) between the ages of 18-60 with no record of surgery in the EDW. We will also recruit individuals with LBP who are not seeking care with flyers and ads in the community.

At the University of Alberta we will recruit from clinics that have been used successfully in the past. These include general practice, physical therapy and chiropractic clinics within the main campus community. University of Alberta already has IRB-approved recruitment materials that have been used in these clinics previously and can be further distributed to potential participants through various approved electronic distribution services. We will also work with the various professional associations to identify patients with specific characteristics using established communication strategies (e.g. patient newsletters and social media postings). As is the case in Utah, potential participants informed by these means will contact research personnel directly to establish eligibility and will align with ICD-10 code related to non-specific LBP (M54.5, M54.9, M51.36) between the ages of 18-60 with no record of surgery.

Individuals interested in participation will meet the site study coordinator to insure eligibility. Reasons for non-enrollment will be tracked. Eligible subjects choosing to participate will sign an informed consent document approved by the University of Utah or Alberta IRB, after which baseline examination procedures and completion of all eligibility assessments will be performed by a Research Assistant who will remain blinded to the subject's treatment group assignment throughout the study. Following baseline examination, all subjects will begin phase I treatment. All assessment and treatment sessions will be conducted at the Patient Wellness Center at the University of Utah and in the Rehabilitation Robotics Sandbox at the University of Alberta. Treatment will be provided by clinicians licensed to provide SMT (DC or PT) and trained in study-related procedures.

5. STUDY INTERVENTIONS

5.1 Interventions, Administration, and Duration

5.1.1 Spinal Manipulative Therapy

The same SMT procedure will be used in phases I and II. Our past work has found equivalent outcomes regardless of SMT technique, thus we will standardize our technique consistent with our past work. This SMT technique has been applied successfully at both performance sites. All SMT sessions will begin with a brief assessment followed by SMT. The subject is supine. The clinician stands opposite the side to be manipulated and side-bends the subject away from the clinician. The side to be manipulated is the side the subject identifies as more painful. If the subject cannot identify a more painful side the clinician selects a side. The subject interlocks their fingers behind the head. The clinician rotates the subject, and delivers a high-velocity, low-amplitude (HVLA) thrust to the anterior superior iliac spine in a posterior/inferior direction. The clinician notes if a cavitation (ie, a "pop") occurred. If it does, SMT treatment is complete. If no cavitation occurs, the subject is repositioned and SMT is performed again. If no cavitation occurs on the second attempt, the clinician will manipulate the opposite side. A maximum of 2 attempts per side is permitted. If no cavitation is noted by that time, SMT treatment is complete. The number of SMT attempts will be recorded by the clinician. Our previous research found no difference in outcome between this SMT procedure and a side-posture HVLA technique. We will permit substitution with side-posture HVLA if the preferred technique is not possible due to subject preference or comfort. In prior research we found the supine and side-posture HVLA techniques well-tolerated with no adverse events.

5.1.2 Multifidus Exercises

Subjects randomized to receive multifidus exercises will begin with isometric multifidus contractions in different positions with clinician feedback and exercises to isometrically co-contract the multifidus and deep abdominal muscles. These exercises have been shown to be effective for activating the multifidus. Subjects will also perform lumbar extensor strengthening exercises shown to produce 20%-50% of multifidus maximum voluntary contraction. This dose is adequate to enhance multifidus activation, without imposing high loads that may exacerbate LBP. Subjects will continue to perform isometric exercises throughout treatment. We have applied these exercises in prior research with no adverse events.

Activity	Description	Initial Dose	Goals for Progression
Preferential, isometric multifidus activation exercises	1. Isolated multifidus contraction while prone, seated, standing 2. Isolated co-contraction of multifidus and deep abdominals in sitting, standing	5 repetitions, 10 sec. hold with normal breathing (each exercise)	progress toward 10 repetitions, 10 sec. hold, perform 2-3x daily
General lumbar extensor and multifidus activation exercises	1. Quadruped single arm raises 2. Side-support exercise	10 lifts, 5 sec. hold each arm 10 repetitions 5 sec. hold each side	progress towards 20 lifts, add arm+leg lift progress towards 20 repetitions

Activity	Description	Initial Dose	Goals for Progression
(subjects prescribed no more than 2 exercises at a time)	3. Bridging while hook-lying 4. Prone single leg lift 5. Prone trunk lift	10 repetitions, 5 sec. hold 10 lifts, 5 sec. hold each leg 10 lifts, 5 sec. hold	progress towards 20 repetitions progress towards 20 lifts, add arm+leg lift progress towards 20 lifts
			Table. Multifidus activation exercise protocol

5.1.3 Mobilizing Exercises

Subjects randomized to receive mobilizing exercises during phase II will be instructed in a program of repeated movements progressing into end-ranges of spinal flexion and/or extension based on principles described by McKenzie, and shown in past studies to reduce spinal stiffness. Subjects will be instructed in mid-range exercises and will be further assessed for a directional preference. A directional preference is present if movement in a particular direction decreases LBP intensity or causes symptoms to centralize towards the midline. Directional preference can be determined reliably and if present, matching the direction of mobilizing exercise to the directional preference improves outcomes. If a subject has a directional preference he or she will be prescribed exercises specifically in that direction along with mid-range exercise. Otherwise the subject will be assigned exercises moving into either flexion or extension based on the clinician's discretion. Subjects will perform their prescribed exercises following SMT at treatment sessions and will be instructed to perform the exercises daily on other days. We have applied these exercises in prior research with no adverse events.

Activity	Description	Initial Dose	Goals for Progression
Mid-range spinal mobility exercises	1. Supine pelvic tilts to promote lumbar flexion/extension 2. Quadruped rocking into lumbar flexion/extension 3. Supine to side lying rotational mobilizations 4. Sitting rotational mobilizations 5. Flexion/Extension	10-20 repetitions each direction performed daily (each exercise)	Full, pain-free ROM, progress to 40 repetitions throughout the day
Exercises specifically into spinal flexion	1. Supine pelvic tilt 2. Quadruped rocking into lumbar flexion 3. Double knee-to-chest while supine 4. Standing flexion 5. Seated flexion 6. Self mobilization into flexion	10-20 repetitions performed daily (prescribe 2 exercises)	Full, pain-free ROM, progress to 40 repetitions throughout the day
Exercises specifically into spinal extension	1. Supine pelvic tilt 2. Quadruped rocking into lumbar flexion 3. Supported on elbows while prone 30 sec 4. Prone press-ups to extended elbows 5. Prone press-ups to extended elbows with exhale 6. Extension while standing 7. Extension in standing with self over pressure	10-20 repetitions performed daily (prescribe 2 exercises)	Full, pain-free ROM, progress to 40 repetitions throughout the day

Table. Stiffness exercise protocol

5.2 Concomitant Interventions

5.2.1 Allowed Interventions

Interventions permitted during the study period include use of medication to control LBP symptoms (NSAIDs, muscle relaxants, etc.) The use of various medications will be recorded at the baseline examination. Visits to health care providers for LBP are allowed during the study period (e.g., physician visits) as long as no interventional procedures are received (e.g., spinal manipulation, massage, exercise therapy, etc.)

5.2.2 Prohibited Interventions

Prohibited interventions during the study period include any mind-body or other interventional procedures including spinal manipulation, massage, exercise therapy, acupuncture, spinal injections, surgical procedures, etc. If any prohibited events occur these will be recorded as off-protocol events. Subjects will continue to participate in study-related treatments and assessments unless the off-protocol intervention changes the risk-benefit profile for the subject.

5.3 Adherence Assessment

Treatment adherence will be assessed based on attendance at scheduled treatment sessions and compliance with treatment protocols during treatment sessions. Once enrolled, a participant will have forms in REDCap for each scheduled treatment session according to the participant's randomized group assignment. Treatment session forms will permit an evaluation of the number of scheduled sessions attended by each participant. For sessions that are attended, the treating clinician will information on the interventions provided and any reasons for non-adherence to protocols. The site study coordinator will monitor the forms at least monthly and discuss instances of non-adherence with the clinician. All off-protocol events will be recorded, such as the use of use of modalities (heat, cold, ultrasound, etc.), or application of manual therapy or exercise procedures not outlined in the protocol. For purposes of the data analysis per-protocol analyses we will define "adherence" as occurring when at least 80% of scheduled treatment sessions are attended. Attendance at <80% of scheduled sessions will be considered a protocol deviation.

6. STUDY PROCEDURES

6.1 Schedule of Evaluations

Assessment	Screening Assessment (Day -7 - 0)	Baseline Assessment, Visit 1 (Day 0)	TX Visits 1-2 (Days 0-7)	1 Week Follow-Up (Day 7-10)	TX Visits 3-8 (Days 8 – 35)	4 Week Follow-Up (Day 29-42)	3 Month Follow-Up (Day 83-97)
Informed Consent Form		X					
Eligibility Criteria	X	X					
Demographics		X					
Medical History		X					
Physical Examination		X		X		X	X
Enrollment		X					
Self-Report Questionnaires							
Oswestry Disability Index	X*	X*		X		X	X
Numeric Pain Rating		X		X		X	X
Psychological Covariates (FABQ, PSESF, PCSF)		X		X		X	X
Global Rating of Change						X	X
Spinal Stiffness Assessment			X	X		X	X
Multifidus Assessment			X	X		X	X
Adverse Events/Side Effects				X		X	
Randomization				X			
Treatment Session Form			X		X		

*Oswestry is to be administered once between screening and baseline, or twice if needed at clinician discretion or if > 7 days has passed since first Oswestry completed.

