6.2 Description of Evaluations

6.2.1 Screening Evaluation

Individuals who contact the site Study Coordinator will be provided information about the study. The Study Coordinator will confirm that the individual is between age 18-60 and is not receiving other interventional or mind-body procedures for their LBP. If the individual is interested in learning more about the project a baseline assessment will be scheduled to obtain informed consent, insure all eligibility criteria are met and schedule a full assessment to begin the study either at that time or within 7 days of the screening evaluation. Before the scheduled baseline assessment, the participant may complete the Oswestry Disability survey to determine if their score is $\geq 20\%$. If the Oswestry score is $< 20\%$, the participant will be notified that they are ineligible for the study and the assessment cancelled.

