6.2.1.1 Consenting Procedure

Interested individuals who are scheduled for a baseline assessment will begin the assessment by providing written informed consent using a form approved by the site institutional review board. The consenting process will be conducted by a research assistant who is trained by the Principal Investigator at the site and has completed Biomedical Research Training for Human Subjects research through the Collaborative Institutional Training Institute (CITI) which includes modules on human subjects research ethics and regulations related to informed consent. A copy of the signed informed consent document will be retained by the researchers. A single consent form will be used for the project. The research assistant consenting the participant will sign an Informed Consent Form (ICF) checklist which will be retained by the researchers.

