6.2.1.2 Screening

Once informed consent is obtained the following screening procedures will be completed within 72 hours to insure eligibility:

- Confirm age on the date of consent is between 18 – 60 years old.
- Confirm that the participant is not aware that she is pregnant.
- Confirm that the participant is not currently receiving other interventions for their LBP.
- Confirm that the participant is experiencing LBP defined as pain between the 12th ribs and buttock with or without symptoms that extend into the buttock(s) or leg(s). without “red flags” suggesting a possible non-musculoskeletal cause (recent trauma, unexplained weight loss, night pain, systemic illness)
- Participant completes the Oswestry disability index to insure the score is $\geq 20\%$
- Research assistant conducts the physical examination to insure no signs of neurologic deficit are present (positive ipsi- or contra-lateral straight leg raise test (symptoms reproduced $<45^\circ$); reflex, sensory, or strength deficit in a pattern consistent with lumbar nerve root compression)

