6.2.2.3 Randomization

Following baseline assessment all participants will receive 2 SMT treatment sessions in the next week. Randomization to additional treatment will be done at the 1-week assessment. A randomization schedule will be developed prior to enrollment by co-investigator [name], Director of the Study Design and Biostatistics Center (SDBC) in the CCTS at the University of Utah. Blocked randomization with block sizes of 4 or 6 will be used. Randomization will be stratified based on site (Utah or Alberta) and responder status after 2 SMT sessions (based on re-assessment of the OSW) to balance these variables. At the 1-week assessment the study coordinator or research assistant will look up the participant in the study database and open the Responder & Randomization Status

form in REDCap. This form will display the Oswestry score from the baseline assessment and the calculation of score change. The percent change between baseline and 1-week scores determines responder status (>50% improvement = “responder”; <50% improvement= “non-responder”). Once the responder status is entered the study staff will select the randomize button on the screen to trigger study assignment based on the allocation table provided by the biostatistician, provided all of eligibility criteria are met and the participant has been assigned to one of the two study sites. If any of these criteria are not valid a warning message will be displayed indicating the criteria issue(s) and the randomization will not be completed.

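### The schedule footnote lets a screening Oswestry up to 7 days old stand as the only pre-treatment score, against the sections that call for one at baseline, so the responder rule can count untreated days

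*Combined protocol and SAP*

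**What the plan says.** Several sections govern the pre-treatment Oswestry.

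- **Section 6.1, footnote:** "Oswestry is to be administered once between screening and baseline, or twice if needed at clinician discretion", or when more than 7 days have gone by since the first one. The table marks the Oswestry under both screening (Day -7 to 0) and baseline (Day 0).
- **Section 6.2.1:** "Before the scheduled baseline assessment, the participant may complete the Oswestry Disability survey to determine if their score is" at least 20%. A lower score makes the person ineligible and the visit is cancelled. The full assessment is scheduled "either at that time or within 7 days of the screening evaluation".
- **Section 6.2.1.1:** "Interested individuals who are scheduled for a baseline assessment will begin the assessment by providing written informed consent". An Oswestry completed before that visit is therefore a pre-consent score.
- **Section 6.2.1.2:** "Once informed consent is obtained the following screening procedures will be completed within 72 hours to insure eligibility". The Oswestry is on that list. Section 6.2.2.1 gives a different outer limit for screening, 7 days.
- **Sections 6.2.2.2 and 9.5.1:** the Oswestry is listed among the measures collected at baseline.
- **Section 6.2.2.3:** for the responder calculation, "This form will display the Oswestry score from the baseline assessment and the calculation of score change". Percent change from baseline to 1 week, against a 50% cut-off, sets responder status.

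Section 4.1 gives the 20% entry criterion without saying which score applies if there are two.

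**The concern.** A participant with one qualifying score from Day -7 satisfies the footnote but not Section 6.2.1.2. Two sites could follow different rules and each point to the protocol in support.

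The consequence falls on responder status, which is meant to describe response after two SMT sessions. It is a stratification factor, the moderator in Secondary Aim 1, and an input to the responder-specific model that Section 9.6 says will be considered under Secondary Aim 2. If the only pre-treatment score predates treatment by up to a week, improvement in that week is credited to SMT, for some participants and not for others.

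The discretionary repeat has no stated criterion. When it is used, nothing says which score settles eligibility.

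**Working it through.** **1. The plan's own figure.** The plan gives no number on this point. Its Oswestry SD is used below, so I first checked that the SD reproduces the sample-size table in Section 9.2. Inputs: SD 14.9, pre-post correlation 0.70, 280 × 0.92 = 257.6 participants, 80% power, two-sided α 0.025.

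Detectable main effect = (2.241 + 0.842) × 14.9 × √(1 − 0.70²) × 2/√257.6 = 4.09, against 4.12 in the table. The SD is being read as the plan uses it.

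**2. The classification window.** The 1-week visit falls on Day 7–10 (Section 6.1) or Day 7–12 (Section 6.2.4).

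- Score taken on Day 0: the window is 7 to 12 days.
- Score taken on Day -7: the window is 14 to 19 days, of which the first 7 precede any treatment. That is 7/19 = 37% to 7/14 = 50% of the window.

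**3. Noise between two scores.** Section 9.5.1 gives a test-retest ICC of 0.90. The standard error of measurement is 14.9 × √(1 − 0.90) = 4.7 points. The SD of the difference between two scores is 4.7 × √2 = 6.7 points. A 6-point difference is therefore ordinary, and it is enough to matter:

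| Screening | Baseline | 1 week | Change from screening | Change from baseline |
|---|---|---|---|---|
| 30 | 24 | 14 | 16/30 = 53.3%, responder | 10/24 = 41.7%, non-responder |
| 24 | 18 | 11 | 13/24 = 54.2%, eligible at entry | 7/18 = 38.9%, below 20% at entry |

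**4. Simulation (2,000,000 draws).** From the plan: SD 14.9 and ICC 0.90. Assumed: normal scores, source mean 24.3 to 35, and proportional Phase I change with mean about 0.40 and SD 0.30. That gives roughly 40% responders, within the 35%–45% of Section 3. Responder class is compared among people scoring at least 20% on both occasions.

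- With no true change between the two scores, about 8% change responder class according to which score is the denominator (0.08 × 280 ≈ 22). Over ICC 0.80 to 0.95 the range is about 6% to 10%.
- With 3 points of improvement before Day 0 (assumed), using the screening score raises the responder rate by about 4.6 points. With 1.5 points (assumed), the rise is about 2.2 points.
- With no true change, 5% to 11% of those at or above 20% on one score fall below it on the other. With 3 points of improvement, 9% to 18% of those eligible at screening would be below 20% on Day 0.

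**5. Scaling.** These figures assume that everyone is affected, and the plan does not say how many would rely on a screening score. If one third did (assumed), the rise in the responder rate would be 2.2/3 = 0.7 points (about 2 of 280) to 4.6/3 = 1.5 points (about 4 of 280).

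**The case against.** Four points on the other side carry weight.

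- **The denominator is named.** A reader might infer that it is undefined whenever two scores exist. It is not: Section 6.2.2.3 uses the score from the baseline assessment, so a second score taken at that visit governs. Only the lone screening score is unresolved.
- **Retesting people who fail the pre-visit screen.** A reader might infer that a clinician could repeat the questionnaire until someone scoring 14–18% qualifies. In the simulation 38% to 45% of such people would reach 20% on a repeat with no true change. Section 6.2.1 closes that route for pre-visit scores, because a score under 20% cancels the visit. At most it stays open for a first score taken at the visit itself, and the footnote does not suggest the repeat is meant for that. The figure also cannot be combined with 3 points of improvement, under which crossing falls to roughly a quarter.
- **Most sections already point to a baseline score.** This is so, and it makes the defect an inconsistency that is cheap to remove. It does not make the footnote harmless, since the schedule is what staff work from.
- **The fix leaves natural recovery in the responder definition.** Phase I has no control group, and the 1-week window already varies by up to 5 days. That stands. The fix removes only the extra lag of up to 7 untreated days that some participants would carry.

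**Conclusion.** The contradiction is real and should be reconciled. The footnote permits a lone, pre-consent screening score up to 7 days old and a repeat without a criterion. Sections 6.2.1.2, 6.2.2.2, 6.2.2.3 and 9.5.1 describe a score taken after consent or at baseline. Two gaps follow: the responder denominator when only a screening score exists, and the score that decides the 20% criterion when two exist.

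The consequence is limited. A reader might infer that the component comparisons are biased. They are not, because all these scores precede randomisation and Section 9.6 takes the 1-week score as the model baseline. What is affected is who enters, the make-up of the responder strata, Secondary Aim 1 (which the plan calls exploratory) and the optional responder-specific model in Secondary Aim 2.

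The sizes (about 8% changing class, a rise of about 2 to 5 points in the responder rate) are upper illustrations. They rest on assumed score distributions, an assumed 1.5 to 3 points of pre-treatment improvement that no section documents, and every participant being affected.

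**What to change.** Align the Section 6.1 footnote with Sections 6.2.1, 6.2.1.2 and 6.2.2.3:

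- Every participant completes an Oswestry at the baseline visit, after consent and before the first SMT session.
- That score is the only denominator for responder status, and is named as the score to which the existing 20% criterion applies.
- A pre-visit score is used only to cancel ineligible visits, as Section 6.2.1 already does.
- The undefined discretionary repeat is removed.

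The cost is one short questionnaire repeated by those who were pre-screened, a wording change in the schedule and the REDCap form, and a few more screen failures on Day 0.
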